### **13.4 Interim Toxicity Monitoring Plan**

The primary endpoint for the interim toxicity monitoring rule of the study will be the occurrence of a Cycle 1 DLT that is attributable to palbociclib or ganitumab or the combination, as defined in Section 5.4.1. To be evaluable for the interim toxicity monitoring rule of Cycle 1 DLTs, a patient must receive at least one dose of either drug and have been followed for at least 30 days following the last dose of protocol therapy or to the start of Cycle 2, whichever occurs first. Additionally, any patient with Cycle 1 DLT will be considered evaluable for the interim toxicity monitoring rule. Cohorts A and B will have separate toxicity monitoring rules as the rate of DLTs is expected to differ by cohort due to differences in frontline therapy for patients in each cohort.

Toxicity as graded by CTCAE v5.0 will be recorded and monitored throughout all cycles of therapy. The number and proportion of toxicities will be tabulated by type, grade, and attribution. A given toxicity will be counted only once in a given patient, at the highest grade observed.

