#### **13.4.1 Cohort A toxicity monitoring plan**

For Cohort A, the original two-stage toxicity monitoring rule was triggered with 2 DLTs out of the first 3 evaluable patients. A new one-stage design has been developed for the remaining 12 patients, all of whom will be treated at a lower dose level than the first 3 patients (contingency A, see Section 5.4.2).

Enroll up to 12 toxicity evaluable patients. If at any time 3 or more patients have a first cycle DLT, enrollment will be paused, the trial will be reviewed by the study committee and the DSMC, and a lower dose level will be considered as outlined in Section 5.4.2. If fewer than 3 of 12 patients have a first cycle DLT, the dose level will be considered sufficiently safe for further study. This rule has the following operating characteristics. The null hypothesis is that the proportion of patients with a Cycle 1 DLT is  $\geq 39\%$  versus the alternative that the proportion with a Cycle 1 DLT is  $\leq 9\%$ . The power is 91.3% and the type 1 error is 9.5%.

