#### **13.4.2 Cohort B toxicity monitoring plan**

For Cohort B, we will utilize the following one-stage toxicity monitoring rule:

Enroll up to 12 toxicity evaluable patients. If at any time 3 or more patients have a first cycle DLT, enrollment will be paused, the trial will be reviewed by the study committee and the DSMC, and a lower dose level will be considered as outlined in Section 5.4.2. If fewer than 3 of 12 patients have a first cycle DLT, the dose level will be considered sufficiently safe for further study. This rule has the following operating characteristics. The null hypothesis is that the

proportion of patients with a Cycle 1 DLT is  $\geq 39\%$  versus the alternative that the proportion with a Cycle 1 DLT is  $\leq 9\%$ . The power is 91.3% and the type 1 error is 9.5%.

The number and proportion of toxicities will be tabulated within each cohort, by type, grade, and attribution. A given toxicity will be counted only once in a given patient, at the highest grade observed.

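### The Cycle 1 DLT rule requires follow-up but no minimum exposure, so DLT-free patients who stop early can fill the 12 slots and raise the chance of calling an unsafe dose safe above 9.5%

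*Combined protocol and SAP*

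**What the plan says.** Section 13.4 sets two conditions that must both hold: "a patient must receive at least one dose of either drug and have been followed for at least 30 days following the last dose". In full, the second condition is that the patient was "followed for at least 30 days following the last dose of protocol therapy or to the start of Cycle 2, whichever occurs first". A further sentence protects the event count: "any patient with Cycle 1 DLT will be considered evaluable for the interim toxicity monitoring rule". No share of the planned Cycle 1 doses is required, and neither is receipt of both agents.

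Sections 13.4.1 and 13.4.2 apply the same rule to each cohort. The size is "Enroll up to 12 toxicity evaluable patients". The boundary is "If at any time 3 or more patients have a first cycle DLT, enrollment will be paused". The favourable conclusion is "If fewer than 3 of 12 patients have a first cycle DLT, the dose level will be considered sufficiently safe for further study". The hypotheses are a Cycle 1 DLT proportion of at least 39% (unsafe) against at most 9% (acceptable), and the operating characteristics are "The power is 91.3% and the type 1 error is 9.5" percent.

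Section 1.1 describes evaluability for toxicity by the one-dose condition alone and does not repeat the follow-up condition. Planned Cycle 1 treatment (Section 5.1.1) is 21 daily palbociclib doses and two ganitumab infusions.

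**The concern.** The rule is meant to judge the Cycle 1 DLT rate of the combination. A patient who takes a single dose of one agent, leaves treatment for a reason unrelated to toxicity (Section 5.6 lists progression, intercurrent illness, non-compliance and withdrawal) and completes 30 days of follow-up is counted as one of 12 patients without a DLT. The binomial figures give that patient the same DLT probability as someone who completed the cycle.

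Follow-up does not fully close the gap. Some DLT criteria in Section 5.4.1, such as a delay of more than 14 days in starting the next cycle, cannot be met by a patient already off treatment. The calendar in Section 10 asks for blood counts twice weekly in Cycle 1, but after treatment ends it schedules only an end-of-therapy visit and a visit at about 30 days. Grade 4 neutropenia or thrombocytopenia of any duration is a DLT in patients without marrow disease, so less frequent sampling can miss events.

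Patients with a DLT are evaluable whatever their exposure, so the dilution affects only the DLT-free count. If risk is lower in short-exposure patients, the error runs one way, towards accepting a dose that is too toxic. The combination has not been given before (Section 1.1), and Cohort A admits patients with relapsed or refractory disease and performance status down to 50%, so some early exits are plausible.

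**Working it through.** **Inputs from the plan.** n = 12 toxicity-evaluable patients per cohort; the dose is accepted with 0–2 DLTs; unsafe rate 39%; acceptable rate 9% (Sections 13.4.1 and 13.4.2).

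**Inputs that are assumed.** The documents give neither k, the number of the 12 who have short exposure, nor f, their DLT risk as a fraction of the full-exposure risk. The range used is k = 1 to 3 and f = 0, 0.5 and 0.75.

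**Step 1: reproduce the stated figures.** Pausing whenever the third DLT occurs gives the same acceptance probability as a fixed count of 12, namely P(X ≤ 2).

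- At 39%: 0.0027 + 0.0204 + 0.0716 = 0.0946, which is the stated 9.5%.
- At 9%: 0.3225 + 0.3827 + 0.2082 = 0.9134, which is the stated 91.3%.

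Both figures are correct for 12 patients with a common rate.

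**Step 2: allow k short-exposure patients.** Let each have DLT probability 0.39f and the other 12 − k have 0.39. Then

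P(accept) = Σ over j = 0, 1, 2 of P[Bin(k, 0.39f) = j] × P[Bin(12 − k, 0.39) ≤ 2 − j].

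Worked case, k = 1 and f = 0.5, so that 0.39f = 0.195:

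- P[Bin(11, 0.39) ≤ 2] = 0.1328
- P[Bin(11, 0.39) ≤ 1] = 0.0044 + 0.0306 = 0.0350
- P(accept) = 0.805 × 0.1328 + 0.195 × 0.0350 = 0.1069 + 0.0068 = 0.1137

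With f = 0 the formula reduces to P[Bin(12 − k, 0.39) ≤ 2].

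| Short-exposure patients among 12 | No DLT risk (f = 0) | Half the risk (f = 0.5) | Three quarters of the risk (f = 0.75) | Same risk (f = 1) |
|---|---|---|---|---|
| 0 | 9.5% | 9.5% | 9.5% | 9.5% |
| 1 | 13.3% | 11.4% | 10.4% | 9.5% |
| 2 | 18.4% | 13.6% | 11.5% | 9.5% |
| 3 | 25.1% | 16.2% | 12.6% | 9.5% |

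At the acceptable rate of 9%, the probability of acceptance goes up rather than down (for example 94.6% with k = 2 and f = 0). The whole cost is therefore on the false-safe side.

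**Step 3: effect of replacement on the response test.** Under Section 13.3.1 a patient with clinical progression is evaluable for response. If such a patient is replaced for the toxicity rule and everyone is then analysed for response with the boundaries unchanged, the response type 1 error grows:

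- Cohort A, P(X ≥ 4) at 10%: 5.6% with 15 patients; 6.8%, 8.3% and 9.8% with 16, 17 and 18.
- Cohort B, two-stage rule at 4%: 7.0% with 7 + 5 patients; 7.7%, 8.4% and 9.0% with one, two or three extra patients in stage 2.

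**Step 4: room for replacements.** Section 13.2 requires 15 + 12 = 27 response-evaluable patients and allows at most 33, which leaves 33 − 27 = 6 places.

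**The case against.** A reader might infer two stronger things, and the documents support neither.

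- **That one dose alone makes a patient DLT-free.** It does not. Section 13.4 also requires the follow-up, so a patient without a DLT who is lost before 30 days and before Cycle 2 is not counted. Only Section 1.1, read alone, suggests otherwise.
- **That 9.5% is a wrong figure.** It is exact for 12 patients at 39%. If 39% is read as the rate among patients evaluable under this definition, it needs no correction. The increase depends on how many patients stop early and how far their risk falls, and the documents give neither.

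The no-risk column is an upper limit, not an expectation. An infusion reaction (Section 6.4.3) can occur at the first infusion, and patients who stop are still observed for 30 days. The half-risk and three-quarter-risk columns belong beside it.

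The context should not be overstated either. The two DLTs in the first three Cohort A patients arose at a higher palbociclib dose than the one the current rule monitors. In SDH-deficient GIST, Section 2.4 reports median PFS of 10 months in each of two earlier studies, so progression within Cycle 1 should be less common in Cohort B.

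Other safeguards exist: DSMC review up to four times a year or more often (Section 12.2), review after any toxic death (Section 5.4.2), and toxicity recording in all cycles. They limit the consequences, but they do not give the 12-patient rule the error rate it quotes when some of the 12 had little exposure.

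What remains is that no minimum exposure is stated. The protocol already accepts that some patients cannot inform part of the rule: Section 5.4.1 makes those with marrow disease at entry not evaluable for hematologic DLT. It does not address patients with little exposure.

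**Conclusion.** The point holds as a gap in the evaluability definition, not as an arithmetic error. A DLT-free patient with very little Cycle 1 treatment can take one of the 12 slots. The quoted false-safe probability of 9.5% applies when all 12 carry the 39% rate. With one or two short-exposure patients it becomes about 11–14% at half the risk and 13–18% at no risk; with three, 16–25%. If nobody stops early, or if risk does not depend on exposure, it stays at 9.5%. The number of early stoppers and their residual risk are assumptions. The direction is not in doubt whenever their risk is lower. Because patients with a DLT are always evaluable, a minimum-exposure condition would lose no events. The change is worth making, since the rule leads directly to a statement that the dose is sufficiently safe.

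**What to change.** For the Section 13.4 rule only, count a patient without a DLT only if that patient received both agents and a pre-specified minimum share of the planned Cycle 1 doses, or missed doses because of drug-related toxicity. The sponsor should set the threshold; the documents offer no basis for a particular value. Keep the existing sentence under which any patient with a Cycle 1 DLT is evaluable regardless of exposure.

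Replace the other patients for this rule within the maximum of 33, and keep them in the safety tables. State that the response analysis uses the first 15 response-evaluable patients in Cohort A and the first 12 in Cohort B, so that replacement for toxicity does not change the response error rates. Align the toxicity-evaluability sentence in Section 1.1 with Section 13.4.

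The cost is protocol wording and possibly a few extra patients. They would come from the six spare places, which also have to cover replacements for patients not evaluable for response.

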#### **13.4.1 Cohort A toxicity monitoring plan**

For Cohort A, the original two-stage toxicity monitoring rule was triggered with 2 DLTs out of the first 3 evaluable patients. A new one-stage design has been developed for the remaining 12 patients, all of whom will be treated at a lower dose level than the first 3 patients (contingency A, see Section 5.4.2).

Enroll up to 12 toxicity evaluable patients. If at any time 3 or more patients have a first cycle DLT, enrollment will be paused, the trial will be reviewed by the study committee and the DSMC, and a lower dose level will be considered as outlined in Section 5.4.2. If fewer than 3 of 12 patients have a first cycle DLT, the dose level will be considered sufficiently safe for further study. This rule has the following operating characteristics. The null hypothesis is that the proportion of patients with a Cycle 1 DLT is  $\geq 39\%$  versus the alternative that the proportion with a Cycle 1 DLT is  $\leq 9\%$ . The power is 91.3% and the type 1 error is 9.5%.

#### **13.4.2 Cohort B toxicity monitoring plan**

For Cohort B, we will utilize the following one-stage toxicity monitoring rule:

Enroll up to 12 toxicity evaluable patients. If at any time 3 or more patients have a first cycle DLT, enrollment will be paused, the trial will be reviewed by the study committee and the DSMC, and a lower dose level will be considered as outlined in Section 5.4.2. If fewer than 3 of 12 patients have a first cycle DLT, the dose level will be considered sufficiently safe for further study. This rule has the following operating characteristics. The null hypothesis is that the

proportion of patients with a Cycle 1 DLT is  $\geq 39\%$  versus the alternative that the proportion with a Cycle 1 DLT is  $\leq 9\%$ . The power is 91.3% and the type 1 error is 9.5%.

The number and proportion of toxicities will be tabulated within each cohort, by type, grade, and attribution. A given toxicity will be counted only once in a given patient, at the highest grade observed.

### **13.5 Analysis of Secondary Efficacy Endpoints**

Progression-free survival (PFS) will be defined as the time from study enrollment to first episode of disease progression or death due to disease, with patients without event censored at last follow-up. Overall survival (OS) will be defined as the time from study enrollment to death, with surviving patients censored at last follow-up. PFS and OS will be estimated using Kaplan-Meier methods separately for each cohort, with standard errors according to Greenwood.

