### 1.3 Secondary Objective

1.3.1 To estimate progression-free survival and overall survival in patients with relapsed or refractory Ewing sarcoma as well as in the separate cohort of patients with SDH-deficient GIST treated with the combination of palbociclib and ganitumab.

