## 11 MEASUREMENT OF EFFECT

The primary endpoint of the study will be assessed by the below criteria. See Section 10 for required disease staging at study entry, after initiation of protocol therapy and during follow-up. Confirmatory scans will also be obtained a minimum of 4 weeks following initial documentation of an objective response.

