### 11.1 Key Definitions

Duration of overall response: The duration of overall response is measured from the time measurement criteria are met for CR or PR (whichever is first recorded) until the first date that recurrent or progressive disease is objectively documented (taking as reference for progressive disease the smallest measurements recorded since the treatment started, or death due to any cause. Participants without events reported are censored at the last disease evaluation).

Duration of overall complete response: The duration of overall CR is measured from the time measurement criteria are first met for CR until the first date that progressive disease is objectively documented, or death due to any cause. Participants without events reported are censored at the last disease evaluation.

Duration of stable disease: Stable disease is measured from the start of the treatment until the criteria for progression are met, taking as reference the smallest measurements recorded since the treatment started, including the baseline measurements.

Progression-Free Survival: Progression-Free Survival (PFS) is defined as the time from registration to the earliest time of progression or death due to any cause. Participants alive without disease progression are censored at date of last disease evaluation.

Overall Survival: Overall Survival (OS) is defined as the time from registration to death. Participants alive are censored at date of last follow-up.

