### 13.1 Study Design/Endpoints

#### 13.1.1 Study Design

The efficacy of the combination of palbociclib and ganitumab will be assessed separately within each cohort, using a one-stage design for Cohort A, and a two-stage design for Cohort B. The primary endpoint is a patient's objective overall response as defined in Section 11. A "responder" is defined as a patient having a confirmed overall response of  $\geq$  PR.

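### Sections 11.1 and 13.5 define PFS differently (which deaths count and where patients are censored), and nothing says which definition governs

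*Combined protocol and SAP*

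**What the plan says.** PFS is one of the two survival endpoints in the secondary objective (Section 1.3: "To estimate progression-free survival and overall survival in patients with relapsed or refractory Ewing sarcoma", and likewise for the GIST cohort). It is defined twice.

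- **Section 11.1** defines PFS as "the time from registration to the earliest time of progression or death due to any cause". Its censoring rule is "Participants alive without disease progression are censored at date of last disease evaluation".
- **Section 13.5** runs PFS from study enrollment to "first episode of disease progression or death due to disease, with patients without event censored at last follow-up".

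For overall survival the two sections agree: "Participants alive are censored at date of last follow-up" in Section 11.1 and "with surviving patients censored at last follow-up" in Section 13.5.

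Two sentences link Section 11 to the analysis, and both concern response only. Section 11 opens with "The primary endpoint of the study will be assessed by the below criteria". Section 13.1.1 says "The primary endpoint is a patient's objective overall response as defined in Section 11". Section 13.5 does not refer to Section 11.1.

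**The concern.** The two sections describe different endpoints. A treatment-related or other non-disease death before progression is a PFS failure under Section 11.1 and a censored observation under Section 13.5. The protocol foresees such deaths: Section 5.4.1 makes attributable Grade 5 toxicity a DLT. Section 13.5 also needs a judgement on cause of death that Section 11.1 avoids.

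The censoring rules can diverge as well. After therapy, scans are left to the local physician (Section 10, note 10), while survival follow-up runs to one year after the last enrolled participant's last dose (Section 5.7), with forms every three months (Section 12.1.2). The last scan and the last contact can therefore be far apart. If last follow-up includes survival contact, a patient who stops without progression or completes 12 cycles is counted as progression-free through time when nobody was required to look.

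The PFS estimate for each cohort is at stake, together with the exploratory ctDNA log-rank test in Section 13.6. In an open-label single-arm trial, two live definitions also allow the choice to be made after the data are seen.

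**Working it through.** **1. The texts side by side**

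| Feature | Section 11.1 | Section 13.5 |
|---|---|---|
| Start | Registration | Study enrollment (probably the same date, since Section 3 enrols through Section 4) |
| Deaths that count | Any cause | Due to disease only |
| PFS censoring | Last disease evaluation | Last follow-up |
| OS censoring | Last follow-up | Last follow-up |

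Section 11.1 uses separate terms for PFS and OS censoring, whereas Section 13.5 uses one term for both. That supports reading it as any contact but does not prove it. If disease follow-up was meant, only the cause-of-death conflict remains.

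**2. Direction**

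Suppose non-disease deaths are censored on the death date and censoring is otherwise the same. The patient then leaves the risk set at the same time under both rules, so without ties

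S(11.1) = S(13.5) × Π(1 − 1/r),

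where the product runs over non-disease deaths and r is the number at risk at each. The Section 13.5 curve is equal or higher. For example, one such death before any other event or censoring multiplies the curve by 14/15 in 15 patients (31.3% becomes 29.2%) or by 11/12 in 12 patients (70.5% becomes 64.6%). Later censoring under Section 13.5 enlarges the risk sets and pushes the same way.

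The order can reverse if a non-disease death is censored at an earlier contact. Take two patients: one progresses at day 80, and the other dies of another cause at day 100, last seen at day 60. At day 80, S = 0.50 under Section 11.1 and 0 under Section 13.5.

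**3. Size**

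The plan gives no PFS figure to reproduce, and no rates of stopping, non-disease death or off-therapy scanning. From the documents come the cohort sizes (15 and 12), the on-therapy scan timing (every 8 weeks, weeks 8 to 48) and a 10-month median PFS for linsitinib (Section 2.4). Everything else is assumed:

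- exponential progression, median 3 or 10 months;
- disease death an exponential time after progression, median 6 or 24 months;
- 20% stop without progression, uniformly over months 0.5 to 6, with a scan at the stop;
- 5% non-disease deaths, uniformly over months 0 to 6, censored on the death date under Section 13.5;
- contact to 24 months;
- no off-therapy progression recorded.

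Six-month PFS, Section 13.5 v Section 11.1 (400,000 simulated patients per scenario):

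| Setting | 3-month median | 10-month median |
|---|---|---|
| Base case | 31.3% v 29.0% (gap 2.3 points) | 70.5% v 64.4% (gap 6.1 points) |
| 50% of off-therapy progressions recorded | 1.9 | 4.8 |
| 80% recorded | 1.6 | 4.0 |
| Only cause of death differs | 1.5 | 3.7 |
| Only censoring differs (no non-disease deaths) | 0.8 | 2.4 |
| Stop/death rates 10%/2% | 1.0 | 2.6 |
| Stop/death rates 30%/10% | 4.4 | 11.2 |

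A simpler model with different assumptions (medians of 2, 4 or 10 months; 0 to 20% of events being non-disease deaths; 0 or 20% of patients lost to scanning) gives gaps from 0 to about 11 points.

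In the 3-month scenario the median PFS is 3.7 months under both rules. In the 10-month scenario it is 17.0 v 10.4 months with no off-therapy progression recorded, and 11.0 v 10.4 with 80% recorded. Other coding of the same assumptions gives 17.5 v 10.7 and 11.0 v 9.2, so these medians are only illustrative.

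**4. How often the texts would differ**

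- At 5% per patient, the chance of at least one non-disease death is at most 1 − 0.95^12 = 46% in 12 patients and 1 − 0.95^15 = 54% in 15. At 2% it is 22% and 26%.
- At base rates the six-month estimates are identical in 49% of simulated 15-patient cohorts (3-month median) and 20% of 12-patient cohorts (10-month median).
- For scale, the binomial standard error is √(0.29 × 0.71/15) ≈ 12 points and √(0.644 × 0.356/12) ≈ 14 points.

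**The case against.** The strongest reply concerns scope and size. Only the cause-of-death conflict is beyond dispute, because last follow-up could mean disease follow-up. The base case also assumes that no off-therapy progression is recorded. Scans after therapy are discretionary, not absent: the Section 10 calendar lists disease evaluation at follow-up, and the note to the overall response table in Section 11.2 asks for efforts to document progression after discontinuation for symptomatic deterioration. The 80% row may be nearer the truth. The remaining rates are assumed, and the 10-month median comes from a different drug. With only cause of death differing and 2% non-disease deaths, the gap is about 0.6 points (3-month) or 1.4 points (10-month), well inside the standard error. PFS is descriptive. Finally, Section 13.5 is as much protocol text as Section 11.1, so strictly the two need only be reconciled.

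Most of this stands as a limit on size. It does not remove the conflict over deaths. The standard error does not excuse the gap either, because both rules score the same patients and, with death-date censoring, any shift goes one way. There are reasons to prefer Section 11.1: it needs no cause-of-death judgement, counts a fatal toxicity as a failure, and does not credit unscanned time.

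**Conclusion.** The concern holds. The conflict over which deaths count is certain. The conflict over censoring follows from the literal wording, but the documents do not settle the intent.

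On the stated assumptions Section 13.5 raises six-month PFS by about 2 to 6 points in the base case, and by 1.5 to 4 points if most off-therapy progression is recorded or only cause of death differs. Across the stop and death rates tried, the range is 1.0 to 11.2 points. The effect is nil if no discordant patient occurs, which is quite possible in cohorts this small. The primary response analysis, sample size and toxicity rules are unaffected. It should be fixed before analysis, but it does not threaten the trial's main conclusion.

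**What to change.** Replace the PFS sentence in Section 13.5 with the Section 11.1 definition: time from registration to first progression or death from any cause, with patients alive and progression-free censored at the last disease evaluation. A cross-reference to Section 11.1 would do equally well.

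Censoring at the last scan after a stop without progression can itself be informative, so also report, by cohort, how many patients were censored after stopping therapy without progression.

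The cost is one sentence and one extra count. No new data or patients are needed. The PFS estimate may be slightly less favourable.
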